11.2 Definition of Trial Analysis Sets

All subjects enrolled in the trial (i.e. subjects for whom informed consent has been obtained and who have been registered in the clinical trial) will be accounted for in the clinical trial report.

All subjects randomised except the first two subjects with a reduced exposure are included in the full analysis set and will be analysed for efficacy. The size of the full analysis set will then be 38 subjects. Exclusions from the full analysis set can be considered in special cases as described in ICH E9, section 5.2.1. Full Analysis Set. If it is decided to exclude a randomised subject from the full analysis set, a justification addressing ICH E9 will be given.

A per protocol analysis set will be defined by excluding subjects from the full analysis set based on the review of protocol deviations before the unblinding of the trial. If it is decided to exclude a subject from the per protocol analysis set, a justification will be given.

A safety analysis set will be defined by excluding subjects from the full analysis set who either received no treatment with investigational product and/or for whom no post-baseline safety evaluations are available.

The decisions regarding inclusion/exclusion of subjects and/or subject data from the trial analysis sets will be documented in the statistical analysis plan update before breaking the randomisation code.

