6.1 Overall Trial Design

This is an exploratory clinical (phase 2a), single-centre, prospective, randomised, vehicle-controlled, double-blinded, intra-individual comparison, split-face model (left/right design) trial. Subjects with moderate to severe acne vulgaris will be treated with LEO 43204 gel 0.018% and vehicle gel (i.e. the Investigational Products (IPs)). The IPs are administered as a thin wet layer to each treatment area (TA) on the left (TA_{left}) and right (TA_{right}) cheeks of the face, each area corresponding to approximately 36 cm² (refer to section [10.2.1](#)). Assessments during the trial are outlined in section [8.1](#).

The subjects will be enrolled sequentially into 4 cohorts (n=40 total).

Progression from one cohort to the next will be decided after a review of LSRs, safety and tolerability by the Safety Review Committee after Week 2 (Visit 7).

Handling of LSRs, safety or tolerability deemed unacceptable is described in section [12](#).

Cohort 1 (n=3): Treatment escalation with once daily application of IPs for one, two and three days respectively for each of the first three subjects.

Subjects will enter treatment sequentially such that the second and third subjects only are exposed after a safety evaluation of the preceding subject is done. The first subject will be dosed for one day only, the second subject up to two days and the third subject up to three days.

The safety evaluation that allows the next subject to be dosed consists of the maximal LSR score from evaluations at days 1, 2, 3, 4, 8 and week 2 or until considerable reduction of LSR score and any treatment related AEs has been observed.

For subjects two and three, the second and third treatment day depends on the following criteria:

- The subject not reporting intolerable response to treatment.
- The investigator not evaluating LSRs or treatment-related AEs to be unacceptable.
- The LSR scores not exceeding predefined criteria (see Table 1, section 6.1).

Subjects not receiving the optional treatment on Day 2 and/or Day 3 due to severe LSRs or treatment related AEs will remain in the trial and attend the scheduled follow up visits.

Cohort 2 (n=6): Once daily treatment for three days with the second and third day optional dependent on predefined criteria (see ‘Treatment Phase’ below) Two subjects may initiate treatment per week. The subjects will follow the same scheduled visits as in cohort 1.

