6.2 Sample Size

A total of 40 subjects (male and female) will be randomised. Subjects withdrawn after randomization will not be replaced.

The expected statistical properties of the primary endpoint are described in section [11.3.4](#).

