11.3.7 Analysis of Safety

The analysis of safety will be based on the safety analysis set.

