- 3 out of 9 subjects with unacceptable LSRs, safety and tolerability events after Cohort 2 (cumulative)
- 5 out of 15 subjects with unacceptable LSRs, safety and tolerability events after Cohort 3 (cumulative)

13 Electronic Case Report Forms and Data Handling

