4.4 Safety

Safety parameters will be evaluated for the safety analysis data set.

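### The safety analysis set is drawn from the full analysis set, so the first two treated subjects are left out of every safety, exposure and demographic table

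*Protocol*

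**What the plan says.** Protocol section 6.2 sets the trial size: "A total of 40 subjects (male and female) will be randomised". Section 6.1 describes the escalation in Cohort 1: "The first subject will be dosed for one day only, the second subject up to two days and the third subject up to three days".

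Section 11.2 then defines the analysis sets in sequence. For the FAS: "All subjects randomised except the first two subjects with a reduced exposure are included in the full analysis set". It gives the result as a number: "The size of the full analysis set will then be 38 subjects". For safety: "A safety analysis set will be defined by excluding subjects from the full analysis set who either received no treatment", or who lack any post-baseline safety evaluation.

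The safety set is used widely:

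- Protocol 11.3.2 uses it for demographics and other baseline characteristics, and 11.3.3 for treatment duration.
- Protocol 11.3.7 states: "The analysis of safety will be based on the safety analysis set".
- SAP 4.4 repeats it: "Safety parameters will be evaluated for the safety analysis data set".
- SAP 4.2 and 4.3 refer back to the protocol for demographics and exposure.

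Nothing in the available text of either document puts the first two subjects back.

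**The concern.** Leaving the first two subjects out of the efficacy analysis is reasonable, since they are not offered the full three-day course. Protocol 11.1 mentions their omission only in connection with efficacy. The same reason does not apply to safety, where anyone exposed should be counted. The plan does not apply it consistently either: a subject in Cohorts 2 to 4 who receives only one or two applications because of a skin reaction stays in the FAS, and therefore in the safety set.

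Safety and tolerability form the secondary objective (4.2), and local skin response (LSR) scores and unacceptable events are secondary endpoints (5.2). Sections 3.3.1 and 3.4 say that the gel has not been given to acne subjects aged 18 to 35 and that there are no data in young adults or in already inflamed skin. The two omitted people are the first exposed in this population. A serious event, an unacceptable LSR or a discontinuation of treatment in either would not appear in the safety tables.

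**Working it through.** **Inputs**

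- Cohort sizes (protocol 6.1): 3, 6, 6 and 25.
- Randomised (6.2): 40.
- Removed from the FAS (11.2): the first two subjects, both in Cohort 1 and both dosed (6.1).
- Safety Review Committee denominators (section 12): 3, 9 and 15, for example "3 out of 9 subjects with unacceptable LSRs, safety and tolerability events after Cohort 2 (cumulative)".
- Power inputs (11.1): n = 38, reductions of 12.4 and 7.3 lesions, SD of the difference 10.4, two-sided 5% paired t-test.

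**Step 1. Reproduce the plan's own figures.**

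- Randomised: 3 + 6 + 6 + 25 = 40.
- FAS: 40 − 2 = 38, as stated.
- Power: δ = 12.4 − 7.3 = 5.1. Noncentrality = (δ/SD) × √n = (5.1/10.4) × √38 ≈ 3.02 on 37 degrees of freedom. The noncentral t distribution gives 83.7%, against 84% stated.

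**Step 2. Size of the safety set as written.** The safety set is the FAS minus untreated subjects and those without post-baseline safety data. It is a subset of the FAS, so its maximum is 38.

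- Share of randomised subjects left out: 2/40 = 5%.
- Share of Cohort 1 left out: 2/3 = 67%.

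**Step 3. Compare with the committee's counts.** Both subjects are in Cohort 1, so each cumulative denominator falls by two when the safety set is applied.

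| Review point | Committee denominator | Safety-set maximum |
|---|---|---|
| After Cohort 1 | 3 | 3 − 2 = 1 |
| After Cohort 2 | 9 | 9 − 2 = 7 |
| After Cohort 3 | 15 | 15 − 2 = 13 |
| All subjects | 40 | 40 − 2 = 38 |

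**Step 4. Effect on a tabulated result.** If an event type occurs in one of the two subjects and nowhere else, the table shows 0/38 = 0% instead of 1/40 = 2.5%.

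If no event occurs in anyone, the one-sided 95% exact upper bound is 1 − 0.05^(1/n):

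- n = 38: 7.6%
- n = 40: 7.2%

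The precision lost is therefore slight. What matters is that exposed subjects, and anything that happened to them, are omitted.

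**Step 5. After the correction.** The safety set can reach 40 and Cohort 1 contributes 3 subjects instead of 1. The FAS remains 38, so the power remains 83.7% (84% stated).

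**The case against.** The strongest reply is that the consequences are limited and the final definition may lie elsewhere.

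- **Other outputs cover the two subjects.** Disposition is reported for all randomised subjects (protocol 11.3.1), so a withdrawal from the trial would be visible there. Section 11.2 promises that all enrolled subjects will be accounted for in the report. The SAP plans listings of all adverse events (4.4.1) and of all data by subject (section 6). Serious events are reported promptly whatever the analysis set, and the committee sees all three Cohort 1 subjects. This stands, and it confines the point to summary tables.
- **The definition may have been corrected.** Section 11.2 leaves decisions on inclusion and exclusion to the SAP update, and the part of the SAP before section 4.1 was not available for this review. A corrected definition there cannot be ruled out. If it exists, the protocol wording still needs to be aligned with it.
- **Matching the committee's counts is not a planned output.** Those denominators belong to blinded interim reviews, and no final tables by cohort are described. This is fair. The mismatch illustrates the omission and is not a separate defect.
- **Short exposure is not wholly unrepresented.** Later subjects may stop after one or two applications and would be counted. That is true, but they stop because of their reaction. The two omitted subjects are the only ones whose exposure is capped below three days by design.
- **The numerical effect is small and the trial is exploratory.** This is also true, but it does not justify a rule that drops exposed subjects from a descriptive safety analysis.

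**Conclusion.** The point holds. Under the definitions in protocol 11.2, the safety set cannot exceed 38, and it excludes two subjects who are dosed by design. That is 5% of those randomised and two-thirds of the escalation cohort. The error carries through to the demographic, exposure, adverse event, LSR and vital-sign summaries. It does not affect the FAS, the primary analysis or the power.

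The conclusion assumes that all 40 subjects are randomised and treated as planned, and that the unavailable opening part of the SAP does not redefine the set. It concerns summary tables only. The wording may be a drafting slip, but a programmer following it would leave both subjects out. It must be corrected before the safety tables are produced.

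**What to change.** In protocol 11.2, and in the SAP wherever the definition is repeated, define the safety analysis set as all randomised subjects who received at least one application of investigational product and have at least one post-baseline safety evaluation. State that it is derived from all randomised subjects and not from the FAS, and that the exclusion of the first two subjects applies to efficacy only. Protocol 11.3.11 already allows such a change through an amendment or the SAP update. If the SAP already contains a corrected definition, point to it and align the protocol text.

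The cost is one sentence. No new data are needed and no efficacy figure changes.

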11.3 Statistical Analysis

11.3.1 Disposition of Subjects

The reasons for leaving the trial will be presented for all randomised subjects by last visit attended.

11.3.2 Demographics and other Baseline Characteristics

Descriptive statistics of demographics and other baseline characteristics will be presented for the safety analysis set.

Demographics include age, sex, race, ethnicity and skin type. Other baseline characteristics include height, weight, BMI and, duration of acne vulgaris, concurrent diagnoses, concomitant medication, previous treatments for acne vulgaris.

11.3.3 Exposure and Treatment Compliance

Descriptive statistics on treatment duration will be provided for the safety analysis set.

11.3.4 Analysis of Primary Endpoints

11.3.4.1 Total lesion count

The evaluation of the treatment effect on total lesion count (inflammatory and non-inflammatory) lesions at Week 12 (primary endpoint) will be performed within the framework of an ANCOVA model with treatment as fixed effect, baseline total lesion count as covariate and subject as random effect.

Comparison between active and vehicle gel will be done by means of a t-test on the estimated treatment contrast in the model. Estimated difference, 95% confidence limit and test probability will together with least square means and their 95% confidence limits be presented from the model.

A sensitivity analysis investigating potential effect of lateral side of lesion will be performed by adding this effect to the above model.

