7.2 Inclusion Criteria

1. Following verbal and written information about the trial, the subject has to provide signed and dated informed consent before any trial-related activities are carried out
2. Subjects should be diagnosed with acne vulgaris of the face.
3. Acne vulgaris disease severity in the full face and in the TA should be scored as moderate to severe (grade 3-4) according to the Investigator's Global Assessment (IGA) Scale (Table 4, section 8.15).

4. Disease severity and total lesion count should be similar in both TAs (with a maximal 2 fold difference in total lesion count).
5. Fitzpatrick skin types I-III (Table 2, section 8.3)
6. Age 18 to 35 years inclusive.
7. Male or female subjects who are otherwise in overall good health including well-controlled diseases (e.g. hypertension, diabetes and thyroid disease) as determined by medical history, physical examination, vital signs (blood pressure, heart rate).
8. Female subjects:
 - of non-childbearing potential, i.e. have a confirmed clinical history of sterility (e.g. the subject is without a uterus or has tubal ligation)OR
 - of child-bearing potential* provided there is a confirmed negative pregnancy test prior to trial treatment to rule out pregnancy AND willing to use effective contraception at trial entry and until completion of the trial.

*Female subjects are considered of child-bearing potential unless they have had a hysterectomy or have undergone tubal ligation.

Effective contraception is defined as follows:

- Abstinence (when this is in line with the preferred and usual life style of the subject).
 - Vasectomised partner (given that the subject is monogamous).
 - An intrauterine device.
 - Double barrier method defined as two distinct methods (two actual barrier methods).
 - Hormonal contraceptive (oral hormonal birth control, oestrogenic vaginal ring, percutaneous contraceptive patches, implants and injectables) for at least one menstrual cycle prior to enrolment.
9. Able to communicate with the (sub)investigator and understand and comply with the requirements of the trial.

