8.15 Investigator Assessments

The investigator assessments will be conducted by an experienced and qualified dermatologist. All assessments of each subject at the site should preferably be performed by the same dermatologist. At Visit 1, identification of the treatment area should be documented on an individual transparent film using three-point landmark technique (refer to [Appendix 10](#)

for details). At all subsequent visits, the transparent film should be used to locate the treatment area for further treatment or assessments of the treated skin.

The following clinical assessments must be made at visits as specified in section 8.1:

1. IGA of the full face (see Table 4 for grading) at Screening to determine acne vulgaris severity for inclusion to the trial at Screening.
2. IGA and non-inflammatory lesion count (open and closed comedones), and inflammatory lesion count (erythematous papules and pustules) in TA_{left} and TA_{right} at Screening and Day 1, Week 2, 4, 8, and 12.
3. LSR assessments (see 8.13) in TA_{left} and TA_{right} using the LSR Grading Scale at Day 1 prior to IP application, and on all subsequent site visits.
4. Skin photography at Day 1, prior to treatment, and on all subsequent site visits (only for cohort 1, 2, and 3).
5. Skin photography at screening for cohort 3 and 4
6. All other skin findings than LSRs and acne will be reported as medical history at Screening or as AEs at subsequent visits.
7. Biomarker and microbiome samplings in Cohort 2, 3 and 4 at Day 1 and at Week 2, 4, 8 and 12. See [Appendix 2](#) and [Appendix 4](#). Samples will be stored for later analysis.

Table 4. Investigator's Global Assessment Scale for Acne Vulgaris*

Grade	Description
0	Clear skin with no inflammatory and non-inflammatory lesions
1	Almost clear; rare non-inflammatory lesions with no more than one small inflammatory lesion
2	Mild severity; greater than Grade 1; some non-inflammatory lesions with no more than a few inflammatory lesions (papules/pustules only, no nodular lesions)
3	Moderate severity; greater than Grade 2; up to many non-inflammatory lesions and may have some inflammatory lesions, but no more than one small nodular lesions
4	Severe; greater than Grade 3; up to many non-inflammatory and inflammatory lesions, but no more than a few nodular lesions

*The same scale will be used for full face and TA evaluation of IGA.

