11.1 Determination of Sample Size

With a sample size of 38 subjects the power of observing a difference between active and vehicle gel will be 84% in a trial with intraindividual comparisons, using a paired two-sided t-test on a 5% level, assuming an approximate total lesion count of 36 at baseline and reductions at end of trial from baseline around 7.3 (20%) and 12.4 (34%) for vehicle gel and active respectively, and a standard deviation of the difference between treatments at end of treatment up to 10.4.

The assumptions on sample size are that all but the two first subjects of the 40 subjects randomised are included in the efficacy analyses, and the assumptions on efficacy rely on experiences from a previous trial conducted by LEO in subjects suffering from acne vulgaris

(LP0045-01), together with an expected reduction in standard deviation of the primary endpoint of at least 20% due to the intraindividual comparisons.

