Investigational product(s)	
LEO 43204 gel 0.018%.
 
Each visit kit should contain 1 tube with active gel and 1 tube with vehicle gel, to be handled in the hospital clinic on Day 1, Day 2 and Day 3, respectively. The label on the tubes will be colored as green to be applied on the right side of the face and red to be applied on the left side of the face.

Investigational reference product(s)	
Vehicle gel. Each kit will be generic and the site personnel will add the randomisation number when assigned to the subject. Each kit contains 2 unit-dose tubes for topical administration

Duration of treatment	
Treatment for up to 3 consecutive days with a follow-up period of 12 Weeks

Main assessments	
Acne lesion (non-inflammatory and inflammatory lesions) counts in treatment areas
 
Investigator Global Assessment of acne severity in treatment areas
 
Tolerability, safety and Local Skin Responses
 
Acne related quality of life and treatment satisfaction questionnaires

Primary endpoint	
Count of total (inflammatory and non-inflammatory) lesions in the treatment area at Week 12.

Secondary endpoint(s)	
Count of inflammatory lesions in the treatment area at Week 12.
 
Count of non-inflammatory lesions in the treatment area at Week 12.
 
Investigator's Global Assessment of the treatment area at Week 12.

Statistical methods	
Lesion count will be analysed by a ANCOVA model with treatment, site and baseline count of total lesions as fixed effects and subject as random effect. Comparison between active and vehicle gel will be done by means of a t-test on the estimated treatment contrast in the model.
 
Investigator Global Assessment will be analysed by descriptive statistics of disease severity by treatment and at Week 12. Descriptive statistics will show frequencies for each score.

For submission to IEC/IRBs and/or regulatory authorities, attach schedule of trial procedures (Section 8.1)

26 Appendix 2: Tape lifting procedure and biomarker analyses

Tape lifting procedure:

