4.3.1 Analysis of primary endpoint

The analysis of the primary endpoint total lesion count at week 12 will follow the description in the protocol. The primary analysis will be based on the FAS analysis set. A sensitivity analysis will include the lateral side of lesion as

a covariate. An additional sensitivity analysis will be performed on the PP analysis set.

Furthermore, if there are missing data then the above analyses will be handled with the below multiple imputation methods and additionally an LOCF and an OC analysis will be included.

Missing data for total lesion count on day 1 or week 12 will be handled using multiple imputation as described in the protocol. The following additional specifications may be given:

- All imputations will be performed by lesion type and treatment group.
- Total lesion will be calculated by summing of inflamed and non-inflamed lesions by simulation

Screening and baseline lesion values are very similar. To avoid problems with identifiability in the estimations modeling will only be from baseline and forward.

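### The primary ANCOVA adjusts a within-subject contrast with a baseline slope that pools between- and within-subject information, and may be less precise than the paired t-test behind the 84% power

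*Protocol*

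**What the plan says.** Protocol 11.3.4.1 analyses total lesion count at Week 12 in an "ANCOVA model with treatment as fixed effect, baseline total lesion count as covariate and subject as random effect", with a t-test on the treatment contrast. SAP 4.3.1 adds no term to the main model: "The analysis of the primary endpoint total lesion count at week 12 will follow the description in the protocol". The only covariate it adds is lateral side, in a sensitivity analysis. Protocol Appendix 1 has the same single baseline covariate and random subject, with a site term added: "ANCOVA model with treatment, site and baseline count of total lesions as fixed effects and subject as random effect".

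Neither document says whether the covariate belongs to the cheek or to the subject. Section 8.15 has both non-inflammatory and inflammatory lesions counted separately in each treatment area ("inflammatory lesion count (erythematous papules and pustules) in TA_{left} and TA_{right} at Screening and Day 1"), so the cheek's own count is the natural reading.

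The sample size in protocol 11.1 rests on a different analysis. It was computed "using a paired two-sided t-test on a 5% level", with 38 subjects, reductions of 7.3 and 12.4 lesions, and an SD of the difference of up to 10.4, giving 84% power. No covariate enters that calculation. Inclusion criterion 4 limits side asymmetry: "with a maximal 2 fold difference in total lesion count".

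**The concern.** With one active and one vehicle cheek per subject, the adjusted treatment estimate is the mean Week 12 difference minus b times the mean Day 1 difference, where b is the fitted baseline slope. Two different slopes feed b. The between-subject slope says how a person's overall count predicts the Week 12 count. The within-subject slope says how the Day 1 difference between cheeks predicts the Week 12 difference. Only the second is relevant to the contrast, but a random-subject model with one covariate averages the two.

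If differences between cheeks fade over 12 weeks while differences between people persist, b is too large for the contrast and the adjustment adds noise. The primary analysis could then have less power than the test used to size the trial.

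**Working it through.** **Stated power.** Difference 12.4 - 7.3 = 5.1 lesions; SD 10.4; n = 38 (all from 11.1). Noncentrality 5.1/10.4 x sqrt(38) = 3.02 on 37 df. Exact two-sided 5% power is 83.7%, so the stated 84% reproduces.

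**The slope used.** Let A be a subject's mean Day 1 count over both cheeks and B the active-minus-vehicle Day 1 difference. In the random-intercept model

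b = w x (between-subject slope) + (1 - w) x (within-subject slope),

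w = (S_A/k) / (S_A/k + S_B), with S_A = 2 x the sum of squares of A about its mean, S_B = half the sum of squares of B about its mean, and k = 1 + 2 x (subject variance)/(residual variance).

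The weight w exceeds one half only when the Day 1 correlation between cheeks is greater than the residual within-subject correlation. The documents give neither. In simulation under assumed inputs, w ranged from about one third to nearly 90%.

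**Effect on precision.** With D the Week 12 difference, s the SD of B and bw the within-subject slope,

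SD(D - bB) = sqrt(10.4² - 2 x b x bw x s² + b² x s²).

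This exceeds 10.4 exactly when b > 2 x bw. The alternative regresses D on B. Its SD is sqrt((10.4² - bw² x s²) x 36/35) on 36 df, where 36/35 is the cost of estimating the slope. Assuming s = 8 and b = 0.6:

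| bw | SD, planned model | Power | SD, D on B | Power |
|---|---|---|---|---|
| 0 | 11.45 | 76.2% | 10.55 | 82.6% |
| 0.1 | 11.11 | 78.7% | 10.52 | 82.9% |
| 0.2 | 10.76 | 81.2% | 10.42 | 83.5% |
| 0.3 | 10.40 | 83.7% | 10.26 | 84.6% |
| 0.4 | 10.02 | 86.3% | 10.04 | 86.2% |
| 0.6 | 9.23 | 91.3% | 9.36 | 90.5% |

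The break-even with the t-test is at bw = 0.3, half of b. In the last row, where the two slopes are equal, D on B costs (9.36/9.23)² - 1, about 3% of variance and 0.8 power points.

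**REML simulations, n = 38, effect 5.1, SD of D 10.4.** All other inputs are assumptions.

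- *With the 2-fold limit applied* (single-cheek baseline SD 10-13, baseline cheek correlation about 0.54-0.85, between-subject slope 0.7): planned-model power was 77-80% at bw = 0, 82-83% at 0.2, 84-87% at 0.35, 85-93% at 0.5 and 88-99% at 0.7. The t-test had about 84%. D on B had 82-85% at bw of 0 or 0.2, and was within about 1 point of the planned model from 0.35 up. With between-subject slope 0.5 and bw = 0.2, the planned model had 83-85%. Type I error in three of these scenarios was 4.5-5.3%.
- *Without the limit* (between-subject baseline SD 12, between-subject slope 0.73, s from 6 to 12, residual SD of the Week 12 subject mean 8): planned-model power was 72-81% at bw from 0 to 0.2, against 82-85% for the t-test and for D on B. At 0.35 or more the planned model matched or beat the t-test.

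**The case against.** The strongest reply is that the planned model may well be the better test. When the two slopes are similar it beats the t-test by up to about 16 points in the simulations that apply the 2-fold limit, a larger swing than the loss of about 7 points there. The 84% is also cautious, because 11.1 calls 10.4 an upper value. At an SD of 9.9, an 11% variance penalty gives an SD of 9.9 x sqrt(1.11) = 10.43 and still about 83.5% power. The trial is an exploratory phase 2a study. And if the covariate were a subject-level baseline, it would cancel from the contrast and the issue would disappear. All of this stands, and it keeps the point to a cheap improvement.

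Several stronger readings are tempting but not supported:

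- *The slope is mostly between-subject.* The weight depends on correlations that the documents do not give, and it fell to about one third in some scenarios. The 2-fold limit does not settle it: around a mean of 36 it still allows 24 against 48.
- *Nothing limits the spread between subjects.* Inclusion criterion 3 requires IGA grade 3-4 in the treatment area, and exclusion criteria 1 and 4 remove some severe disease, although no count range is set.
- *The model over-adjusts.* That requires poor persistence of side differences, which no passage shows. The SAP remark that screening and baseline values are close concerns at most 28 days, so it settles neither side of the 12-week question.
- *The estimate is biased.* Side is randomised. A shift due to chance Day 1 imbalance is the same variance loss seen in a single trial, and should not be counted as a second harm.

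What remains is that the alternative never loses more than about 1 power point in these calculations, while the planned model can lose several.

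**Conclusion.** The point holds as a conditional loss of precision. Read with the own-cheek count, the primary model adjusts a within-subject contrast with a pooled slope, and its power need not equal the 84% computed for the unadjusted paired test. If side differences persist poorly (within-subject slope 0 to 0.2), power is about 72-81% without the symmetry limit and 77-83% with it, when the between-subject slope is about 0.7. If they persist at a slope of 0.35 or more, the planned model is as good as the t-test or better. These ranges rest on assumed baseline SDs, correlations and slopes, so the documents cannot show which case applies. Validity is not in question.

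**What to change.** In protocol 11.3.4.1 and SAP 4.3.1, state that the covariate is the own-cheek Day 1 total lesion count, and add the subject's mean Day 1 count over both cheeks as a second covariate. The own-cheek slope is then estimated within subject. For the treatment contrast this equals regressing the Week 12 active-minus-vehicle difference on the Day 1 difference. Keep the random subject effect for the least-squares means. Where Day 1 counts are imputed, compute the subject mean within each imputed data set.

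The change should be fixed before the randomisation code is broken; after that, it belongs in a labelled sensitivity analysis. SAP 4.3.2 already makes an alignment of this kind, replacing Fisher's exact test with McNemar's because the data are paired.

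The cost is one or two sentences and one derived variable, with no new data. The statistical price is one degree of freedom, and a few percent of variance or about 1 power point if the two slopes are equal.
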